#### 1.3.2 Delamanid

Systemic exposure is greater when delamanid is taken with food: about 2-fold greater with a standard meal and 4-fold greater with a high-fat meal. Peak plasma concentrations are reached in approximately 4 hours postdose, regardless of food intake. The elimination half-life of delamanid is about 30 to 38 hours, allowing steady-state to be reached after 10 to 14 days of dosing. The terminal-phase elimination half-life ( $t_{1/2,z}$ ) of its major metabolite (DM-6705) is approximately 230 hours, and steady-state is reached by 8 weeks.

The single-dose C-delamanid trial indicated that delamanid and its metabolites were predominantly excreted in the feces, while renal excretion is a negligible pathway for elimination. In vitro data suggest that delamanid is essentially metabolized by albumin, resulting in the formation of the primary metabolite DM-6705, which in turn is metabolized to DM-6704 and DM-6706. In vitro metabolism studies in human liver microsomes suggest limited contribution of CYP isoenzymes to the metabolism of delamanid, although CYP isoenzymes appear to be involved in consecutive metabolism. Eight metabolites have been identified in human plasma following multiple oral doses, though present at low concentrations after 10 to 14 days of dosing, representing all together about 1% to 10% of parent delamanid. Delamanid does not show clinically meaningful induction and/or inhibitory effects on CYP isoenzyme activity. Delamanid binds to all plasma proteins (> 99.5%) and most extensively (> 97%) to albumin and lipoproteins. The primary metabolites DM-6704, DM-6705, and DM-6706 extensively

Protocol 323-201-00003

(> 97%) bind to human serum proteins. Delamanid does not show affinity for red blood cells. Delamanid and metabolite PK parameters do not notably vary with gender or race.

Administration of delamanid has been shown to result in QT interval prolongation, an effect associated with delamanid and its metabolites but is most closely correlated with DM-6705 plasma concentrations. DM-6705 accumulates slowly over time to reach maximal concentrations after 6 to 10 weeks of treatment. The QT interval prolongation increased accordingly and reversed upon discontinuation of treatment.

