gConfirmation of acid-fast bacilli (microscopy from smear  $\geq$  1+) and drug-susceptible TB using any combination of Xpert MTB/RIF, line probe assay, culture, and/or epidemiologic history.

hFor HIV positive subjects who are included in stage 2, HIV testing does not need to be repeated at screening if the HIV positive status has been documented prior to screening (within the last month) and the documentation can be kept with the trial documentation for the required duration. For subjects who are HIV positive, blood samples are to be drawn for CD4 assessment at the local laboratory.

iFemale subjects only.

jPostmenopausal female subjects only.

kSerum chemistry, hematology, urinalysis, and coagulation testing will be performed at screening, Day -1, Day 4 (predose), Day 7 (predose), Day 14 (predose), and Day 20 or at ET.

lVital signs (blood pressure, heart rate, temperature, and respiratory rate) will be assessed at screening and on Day -1, Day 1 (predose and at 1, 2, 4, 8, and 12 hours postdose), Days 2 through 6 (predose and 2 and 4 hours postdose), Day 7 (predose and 1, 2, 4, 8, and 12 hours postdose), Days 8 through 13 (predose and 2 and 4 hours postdose), Day 14 (predose and 1, 2, 4, 8, and 12 hours postdose), and Days 15 through 20 or at ET. **At screening**, blood pressure and heart rate will be taken with the subject in the **supine (performed first) and sitting position** after remaining for  $\geq$  3 minutes in each position and temperature and respiratory rate will be taken with the subject in the supine position. At all other time points, vital signs will be obtained after the subject has been at rest in the supine position for at least 1 minute. Vital signs will be obtained prior to the ECG and PK blood draw at the nominal time points, where applicable. The post-dose vital signs could be performed within 15 minutes earlier than the expected post-dose timepoints.

mStandard 12-lead ECGs will be collected in triplicate (5 minutes apart) at screening and on Day -1, Day 7 (predose), and Day 14 (predose). The ECGs will be recorded after the subject has been supine and at rest for  $\geq$  10 minutes prior to the first ECG and subjects will remain supine through the final ECG. Electrocardiograms will be obtained prior to the PK blood draw and after vital signs at the nominal time points, where applicable.

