
On Day 20 (or at ET), the following will be performed:
 
 
• Perform a targeted physical examination.
 
• Measure weight.
 
• Assess vital signs (blood pressure, heart rate, temperature, and respiratory rate). Vital signs will be obtained after the subject has been at rest in the supine position for at least 1 minute.
 
• Collect serum chemistry, hematology, urinalysis, and coagulation clinical laboratory samples.
 
• For subjects randomized to OPC-167832 (stage 1) and/or delamanid and/or BDQ (stage 2), collect a PK blood sample for OPC-167832 only (stage 1) or OPC-167832, delamanid and its metabolite DM-6705, or BDQ and its metabolite M2 (stage 2) at 144 hours after the Day 14 dose.b
 
• Administer treatment for pulmonary TB to all subjects according to the local standard of care regimen (RHEZ).
 
• After completion of the inpatient stay, all subjects must be referred to local community clinics to receive continued treatment for pulmonary TB per the local standard of care regimen.
 
• Provide meals as needed.
 
• Discharge subjects from the trial site.
 

Follow-up (14 ± 3 Days After the Last Dose of Trial Treatment [IMP or RHEZ])
Contact the subjects via telephone for follow-up of AEs and concomitant medication.
Throughout the Trial

The following will be performed from the screening visit through and during the follow-up telephone call:
 
 
• Assess and record AEs
 
• Record prior/concomitant medications (including current oral antipsychotic medication), as applicable.
 

Protocol 323-201-00003

aIn subjects with no clinical indication to start RHEZ immediately, commencement of RHEZ can be delayed for up to 3 days (Days 15, 16, or 17) under close supervision in the trial site hospital ward

bThe Day 20 PK sample will be collected during the ET visit.

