### **3.8.3 Individual Subject Discontinuation**

#### **3.8.3.1 Treatment Discontinuation**

After the first dose of IMP or RHEZ on Day 1, a subject may stop treatment permanently for a variety of reasons. Treatment discontinuations may be initiated by a subject or may become medically necessary due to AEs, required treatment with a disallowed medication or therapy, or other reasons, as determined by the investigator. If a subject discontinues treatment, their participation in the trial will be discontinued. Discontinued subjects should be encouraged to complete all ET and follow-up assessments with ET assessments conducted as soon as possible after the subject is withdrawn.

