#### **3.8.3.2 Documenting Reasons for Discontinuation**

All subjects have the right to withdraw and the investigator can discontinue a subject's participation in the trial at any time if medically necessary.

In addition, subjects meeting the following criteria must be withdrawn from the trial (only one reason for discontinuation [the main reason] can be recorded in the eCRF):

- Death
- TB disease relapse or TB disease progression
- Failure to meet inclusion and exclusion criteria
- Lost to follow-up
- Occurrence of QTcF > 500 msec
- Noncompliance with IMP or RHEZ (if confirmed not related to an AE)
- Physician decision (other than AE)
- Pregnancy (see [Section 5.5](#))
- Major protocol deviation (other than noncompliance with IMP or RHEZ)
- Site terminated by sponsor
- Trial terminated by sponsor
- Withdrawal of consent by parent/guardian (if confirmed not related to an AE)
- Withdrawal of consent by subject (if confirmed not related to an AE)

If the subject discontinues IMP or RHEZ due to an AE, the investigator, or other trial personnel, will make every effort to follow the event until it has resolved or stabilized. Follow-up procedures in [Section 3.8.3.1](#) must be followed. Subjects may be replaced, if discontinuations/withdrawals occur, as described in [Section 3.3](#).

Protocol 323-201-00003

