### 9.6 Electrocardiogram Data

Standard 12-lead ECGs will be collected in triplicate (5 minutes apart) at screening and on Day -1, Day 7 (predose), and Day 14 (predose). The ECGs will be recorded after the subject has been supine and at rest for  $\geq 10$  minutes prior to the first ECG and subjects will remain supine through the final ECG. Electrocardiograms will be obtained prior to the PK blood draw and after vital signs at the nominal time points, where applicable.

Heart rate, ventricular rate, RR interval, PR interval, QRS duration, and QT intervals will be recorded. The QTcF and corrected QT interval using Bazett's method (QTcB) will be calculated.

ECGs are available in triplicates at each nominal timepoint, but may appear as a single or duplicate assessment. All (single, duplicate or triplicate) ECGs at each nominal time point will be averaged and the average will be used in descriptive summary statistics and frequency and percentages. Baseline of ECG is defined as the averaged measurement on Day -1. If the measurement from Day -1 is missing, the screening ECG is taken as baseline.

Summary and change from baseline for ECG will be presented for continuous ECG parameters by visit and treatment group.

Incidence and percentage of potentially clinically significant ECG parameters as defined in Appendix 4 will be presented for each treatment group. All post baseline visit till end of study will be included in incidences of significant change or value. For criteria that involves change from baseline, the subject must have a baseline value to be included in the analysis. For absolute criteria the complete Safety Set will be included.

Incidence of potentially clinically significant QT increases will also be summarized by treatment groups.

In summarizing the incidence of abnormalities, a patient must have had an evaluation that met abnormality criteria by the end of trial, i.e. last contact date. Incidence rate is calculated as the number of patients having at least one abnormality within a trial period divided by the number of patients who are both exposed to trial medication and have an on-treatment evaluation within that trial period.

When the ECG is repeated, the last repeat value will be used in the summary for that visit. Unscheduled ECG data will not be summarized in the change from baseline descriptive analysis but will be included in the incidence of clinically relevant table.

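### SAP 9.6 gives two conflicting denominators for absolute ECG criteria, and the ECG schedule makes it foreseeable that they will differ

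*SAP*

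**What the plan says.** SAP 9.6 treats two kinds of ECG criterion differently. Criteria based on change require a baseline value. For the others, "For absolute criteria the complete Safety Set will be included". Two paragraphs later the section defines the incidence rate as patients with at least one abnormality "divided by the number of patients who are both exposed to trial medication and have an on-treatment evaluation within that trial period". SAP 5.2 admits to the Safety Set anyone who was randomized and took any dose; no ECG is needed.

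On timing, Protocol Table 3.7-1 footnote m reads "Standard 12-lead ECGs will be collected in triplicate (5 minutes apart) at screening and on Day -1, Day 7 (predose), and Day 14 (predose"), and SAP 9.6 repeats the same four occasions: "at screening and on Day -1, Day 7 (predose), and Day 14 (predose"). In Table 3.7.3-1 the final in-clinic visit opens with "On Day 20 (or at ET), the following will be performed" and then lists examination, weight, vital signs, laboratory samples and a PK sample, but no ECG. The laboratory and vital-sign footnotes (k and l) name early termination; footnote m does not.

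Protocol 3.8.3.1 adds: "If a subject discontinues treatment, their participation in the trial will be discontinued". Such subjects are encouraged to complete the early termination and follow-up assessments. Protocol 3.8.3.2 lists "Occurrence of QTcF > 500 msec" among the reasons for mandatory withdrawal.

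**The concern.** A subject who takes at least one dose and leaves before the Day 7 ECG is in the Safety Set but has no scheduled post-baseline 12-lead ECG. One SAP rule puts that subject in the denominator, where no event can be recorded for them. The other rule leaves the subject out. A programmer must choose, and the Safety Set sentence is the one that names absolute criteria. In SAP Appendix 4 the absolute QTcF and QTcB thresholds (above 450 and above 500 msec) carry no change requirement, so the conflict falls on the main QTc categories.

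Incidence of abnormal ECG findings is part of the primary safety endpoint in both stages (Protocol 3.5.1.6), and the combination arms are to be compared with OPC-167832 alone from Stage 1 (Protocol 3.5.2.5). The number of unevaluated subjects can differ between arms, so the dilution would not necessarily cancel in those comparisons.

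**Working it through.** The plan states no ECG incidence, early-stopping rate or ECG evaluability rate, so there is no figure to reproduce. The arm sizes do check: 4 × (14 + 4) + (14 + 14 + 14 + 4) = 72 + 46 = 118, the planned total.

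**Inputs**
- N = 14 per OPC-167832 arm (SAP 3.1). Pooled RHEZ: 4 × 4 + 4 = 20.
- k = dosed subjects with no post-baseline ECG. Assumed range 0 to 3.
- x = subjects with an event. Assumed 1 or 3.

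**Formulas**
- Safety Set rule: x/N.
- Evaluated-subjects rule: x/(N − k).
- Ratio of the first to the second: (N − k)/N, whatever x is.
- Difference: xk / [N(N − k)].

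**Results, N = 14**

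| k | Ratio | x = 1: Safety Set | x = 1: evaluated | x = 3: Safety Set | x = 3: evaluated |
|---|---|---|---|---|---|
| 0 | 1.000 | 7.1% | 7.1% | 21.4% | 21.4% |
| 1 | 0.929 | 7.1% | 7.7% | 21.4% | 23.1% |
| 2 | 0.857 | 7.1% | 8.3% | 21.4% | 25.0% |
| 3 | 0.786 | 7.1% | 9.1% | 21.4% | 27.3% |

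The shortfall for one event is 0.5, 1.2 and 1.9 percentage points at k = 1, 2 and 3. For three events it is 1.6, 3.6 and 5.8 points. In the pooled RHEZ group the ratios are 19/20 = 0.95, 18/20 = 0.90 and 17/20 = 0.85.

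**Can k exceed zero?** Three provisions together allow it: no scheduled 12-lead ECG between the first dose and Day 7, none at early termination, and the end of participation once treatment stops. Protocol 3.3.2 also expects some discontinuations and allows replacement; a dosed subject who is replaced still meets the Safety Set definition. Two things could supply data:
- Unscheduled ECGs. SAP 9.6 counts these toward incidence, so a subject who has one is evaluated. None is required at early termination.
- Holter monitoring on Days −1, 1 and 14. It covers Day 1 for an early stopper, but the SAP uses Holter data in the exposure-response analysis (SAP 11) and does not bring them into the 9.6 incidence table.

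**The case against.** The best defence is that the two sentences can be read together. The Safety Set sentence follows directly on the baseline requirement for change criteria, so it may mean only that absolute criteria carry no such requirement, with the later sentence fixing the rate. That reading is reasonable, and under it nothing is understated. But the text does not say so: it names a complete analysis set for absolute criteria, and the general rule does not say that it overrides this.

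It is also fair that the trial is descriptive and unpowered, that the effect is modest at plausible k, and that stopping early need not signal a cardiac problem, since 3.8.3.2 includes non-medical reasons.

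A reader might infer more than the documents support:
- *That QTc incidence is understated as a matter of fact.* This needs the Safety Set rule to be programmed, at least one dosed subject in the arm without a post-baseline ECG, and at least one event in that arm. It also reaches only absolute criteria, not the change categories.
- *That a subject withdrawn for QTcF above 500 msec drops out of the count.* The ECG that triggered withdrawal already makes that subject a case.
- *That the withdrawal criterion can be met only on Day 7 or Day 14.* It is not limited to scheduled ECGs, and Protocol 3.7.6.4 calls for a repeat when results are clinically significant. The criterion and the schedule sit awkwardly together, but they do not flatly contradict each other.
- *That the schedule's inability to show QT recovery belongs to this point.* Protocol 1.3.2 says of delamanid: "The QT interval prolongation increased accordingly and reversed upon discontinuation of treatment". No objective or endpoint concerns reversal, subjects from the IMP arms are on RHEZ by Day 20, and residual metabolite has no bearing on a denominator.

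**Conclusion.** SAP 9.6 is wrong as written, because it gives two denominators for the same absolute ECG criteria. They agree only when every dosed subject in the arm has a post-baseline ECG. If the Safety Set sentence is applied, incidence is scaled by (N − k)/N: 0.929 to 0.786 for k = 1 to 3 in an arm of 14. If the evaluated-subjects sentence is applied, the effect is zero. The values of k and x are assumptions, so the actual size cannot be fixed from the documents. The contradiction itself depends on no assumption and affects part of a primary safety endpoint. No choice of denominator recovers an ECG that was never taken, which is why the number unevaluated needs to be visible.

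**What to change.** In SAP 9.6:
1. Delete the Safety Set sentence for absolute criteria.
2. Use one denominator for all ECG criteria: dosed subjects with at least one post-baseline ECG, scheduled or unscheduled, plus a baseline ECG for change criteria. Replace the on-treatment-evaluation wording to match; post-baseline also fits the section's own event window, which runs over all post-baseline visits to the end of the study.
3. Show n evaluated/N for each criterion, and report by arm the dosed subjects with no post-baseline ECG.
4. Apply the same rule to the Stage 1 interim tables and the final tables.

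This costs SAP wording and a column in the tables; no new data are needed.

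Separately, the sponsor should reconcile the ECG schedule (Table 3.7-1 footnote m and the Day 20/early termination list in Table 3.7.3-1) with the QTcF withdrawal criterion in 3.8.3.2. How to do so is the sponsor's decision. Any change to scheduled assessments would need a protocol amendment, and if introduced between stages would make ECG ascertainment unequal across a planned comparison.

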13.	Changes in the ECG such as QTcF > 450 msec, atrioventricular block II or III, bi-fascicular block, at screening or current or history of clinically significant ventricular arrhythmias. Other ECG changes if considered clinically significant by the investigator.
14.	Subjects receiving any of the prohibited medications within the specified periods or who would be likely to require prohibited concomitant therapy during the trial.
15.	Female subjects who are breast-feeding or who have a positive pregnancy test result prior to receiving the first dose of IMP or RHEZ on Day 1.
16.	History of significant drug and/or alcohol abuse within 2 years prior to screening.
17.	History of or current hepatitis or carriers of HBsAg and/or anti-HCV.
18.	Positive urine or blood alcohol test and/or urine drug screen for substance abuse at screening (not including cannabinoids).
19.	History of having taken an investigational drug within 30 days preceding trial entry (ie, prior to screening).
20.	A history of difficulty in donating blood.
21.	Donation of blood or plasma within 30 days prior to dosing.
22.	Consumption of alcohol and/or grapefruit, grapefruit juice, Seville oranges, or Seville orange juice and related products within 72 hours prior to the first dose of IMP or RHEZ on Day 1.
23.	History of serious mental disorders that, in the opinion of the investigator, would exclude the subject from participating in this trial.
24.	Any known prior exposure to OPC-167832, delamanid, or BDQ.
25.	Subjects with significant medical comorbidities that in the opinion of the investigator, should not participate in the trial.

Anti-HCV = hepatitis C antibodies; HBsAg = hepatitis B surface antigen.

Subjects excluded for positive drug/alcohol screen are not eligible to be rescreened for participation in the trial. However, subjects excluded for other reasons may be rescreened at any time if the exclusion characteristic has changed. In the event that the subject is rescreened a new ICF must be signed, a new screening number assigned, and all screening procedures repeated.

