#### **3.7.6.4 Standard 12-lead Electrocardiograms**

Standard 12-lead ECGs will be collected in triplicate (5 minutes apart) at the time points presented in the Schedule of Assessments, [Table 3.7-1](#). The mean ECGs of the 3 time points will be utilized to determine subject's eligibility during screening. The ECGs will be collected prior to PK blood draws and after vital signs at the nominal time points, where applicable.

Standard 12-lead ECGs will be recorded after the subject has been supine and at rest for  $\geq 10$  minutes prior to the first ECG and subjects will remain supine through the final ECG. Heart rate, ventricular rate, RR interval, PR interval, QRS duration, and QT intervals will be recorded. The QTcF and corrected QT interval using Bazett's method (QTcB) will be calculated. The 12-lead ECGs will be evaluated at the trial sites to determine the subject's eligibility and to monitor safety during the trial. The principal investigators or designees (licensed physician) will review, sign, and date each ECG reading, noting whether or not any abnormal results are of clinical significance. The ECG will be repeated if any results are considered to be clinically significant. The reviewers must be listed on FDA Form 1572 and the trial site delegation of responsibility form. Electrocardiogram data will be recorded electronically by the central ECG laboratory(ies) and by the trial site(s). Eligibility for the trial will be based on the central ECG report at the screening visit.

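### Using the last repeat in place of a flagged ECG or laboratory value can understate QTcF change and drop an abnormal laboratory result from a primary safety incidence

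*SAP*

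**What the plan says.** **ECG, protocol.** Section 3.7.6.4 instructs sites: "The ECG will be repeated if any results are considered to be clinically significant". It gives no threshold, and the instruction covers any ECG finding, not QTcF alone. After baseline, triplicate 12-lead ECGs are scheduled only before dosing on Day 7 and Day 14 (Table 3.7-1). Screening excludes subjects with "Changes in the ECG such as QTcF > 450 msec" (3.4.3).

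**ECG, SAP 9.6.** Several rules bear on a repeated ECG:
- By-visit summary: "When the ECG is repeated, the last repeat value will be used in the summary for that visit".
- Averaging: all tracings at a nominal time point are averaged, and "the average will be used in descriptive summary statistics and frequency and percentages".
- Unscheduled tracings: "Unscheduled ECG data will not be summarized in the change from baseline descriptive analysis", but they do enter the incidence table.
- Incidence: the numerator is "the number of patients having at least one abnormality within a trial period", taken over all post-baseline visits.
- Baseline: "Baseline of ECG is defined as the averaged measurement on Day -1". The last-repeat rule is not confined to post-baseline visits, so it applies here too.

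**Laboratory.** Protocol 5.1 lets the investigator repeat an abnormal test to check it. SAP 9.3 takes the last repeat within a visit as that visit's value. It keeps unscheduled tests out of mean change but adds them to the search for abnormalities in the incidence and shift analyses. It says nothing about an original that a repeat has superseded.

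**The concern.** Replacement that depends on the outcome is not neutral. A high reading is partly true level and partly chance, and a second reading in the same subject tends to be lower. If high readings are redrawn and the rest are kept, the mean falls. An arm that prolongs QTcF has more readings above any fixed threshold, so it loses more, and its contrast with other arms shrinks. Protocol 1.3.2 states that delamanid prolongs QT, and delamanid is in two Stage 2 arms of 14.

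The incidence of abnormal laboratory and ECG findings is a primary safety endpoint in both stages (protocol 3.5.1.6). With 14 subjects per arm, keeping or dropping one abnormal original changes the reported percentage visibly.

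**Working it through.** The plan states no figure on this point, so there is none to reproduce.

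**1. Formula.** Let Y be the original on-treatment triplicate mean, Y′ an independent repeat, B and B′ the same at Day -1, and T the repeat threshold.

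Understatement of mean change = E[(Y − Y′)·1(Y > T)] − E[(B − B′)·1(B > T)]

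Without the screening exclusion, each term equals (s²/σ)·φ((T − μ)/σ), with σ² = sb² + s². Here sb is the between-subject SD, s the SD of a triplicate mean and φ the standard normal density.

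**2. Inputs.** From the documents: screening limit 450 msec, Day -1 baseline, last repeat replaces, 14 per arm. Assumed, because the documents are silent: baseline mean 410 to 430 msec, sb 15 to 20, s 5 to 10, true rise 0 to 20 msec, T 450 to 480 msec. T = 500 was added because 500 msec is the protocol's only on-treatment QTcF action limit (3.8.3.2).

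**3. Hand check.** Take an on-treatment mean of 435, sb 15, s 8 and T 450. Then σ = √(225 + 64) = 17, s²/σ = 64/17 = 3.76 and φ(15/17) = 0.270, so the shift is 3.76 × 0.270 = 1.02 msec. Simulation without the exclusion also gives 1.02. If original and repeat are averaged, it halves to 0.51.

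**4. Reference case with the exclusion** (baseline 420, rise 15, sb 15, s 8; simulated, msec):

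| T | On-treatment shift | Day -1 shift | Net understatement | Expected QTcF > 450 in 14: originals | Last repeat only |
|---|---|---|---|---|---|
| 450 | 1.011 | 0.242 | 0.770 | 2.25 | 1.25 |
| 460 | 0.446 | 0.046 | 0.400 | 2.25 | 2.07 |
| 470 | 0.112 | 0.005 | 0.107 | 2.25 | 2.24 |
| 480 | 0.014 | 0.000 | 0.014 | 2.25 | 2.25 |

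The Day -1 offset is partial because screening has already removed many subjects with long QTcF.

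**5. Largest net understatement over the grid** (msec):

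| True rise | T 450 | 460 | 470 | 480 | 500 |
|---|---|---|---|---|---|
| 10 | 0.903 | 0.642 | 0.259 | 0.069 | 0.001 |
| 20 | 1.464 | 1.550 | 0.880 | 0.329 | 0.013 |

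With no true rise the two terms cancel (at most 0.01). The smallest values on the grid are essentially 0.

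**6. Sensitivity to the trigger.** A second simulation used means of 405 and 415, sb 16 and s up to 12, with the rule also applied at Day -1. With T 450 it gave up to 0.7 msec at a 10 msec rise and 1.7 at 20. If a rise of 30 msec or more also prompted a repeat, it gave up to 2.9 msec at a 20 msec rise and about 0.6 with no true rise. Triggers of > 500 msec, alone or with a rise > 60 msec, gave at most about 0.2.

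**7. One subject.** 1/14 = 7.1% (95% Clopper-Pearson interval 0.2 to 33.9%). 0/14 = 0% (upper limit 23.2%).

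**8. Laboratory rule, by reading.** Suppose an original ALT is in the Grade 3 range (5.0 to < 10.0 × ULN, SAP Appendix 1) and the same-visit repeat is in the Grade 2 range (2.5 to < 5.0). Under SAP 9.3 the visit value is Grade 2. The original is neither the visit value nor an unscheduled test, so no stated rule brings it into the incidence count.

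**The case against.** **No exclusive trigger.** Protocol 3.7.6.4 does not say that ECGs are repeated solely for clinically significant results. Technical repeats are possible, and a repeat for a rhythm or conduction finding has no predictable effect on QTcF. This stands.

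**Bias not established.** A reader might infer that by-visit QTcF change is biased downward as a matter of fact. The documents do not support that. It requires that long QTcF prompts the repeat, that the repeat replaces the whole triplicate mean, and that the repeat is not classed as unscheduled. If it is unscheduled, SAP 9.6 keeps it out of change from baseline and no bias arises. The trigger is a physician's judgement: 450 msec is an entry limit and a table flag, not a repeat rule.

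**ECG incidence largely settled.** A reader might also infer that replaced ECGs disappear from the Appendix 4 table. The last-repeat sentence concerns the visit summary, and the incidence rules point towards counting the original. That mostly stands. What remains is the averaging sentence, which also governs frequencies and percentages and is not reconciled with the last-repeat rule.

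**Laboratory safeguards.** Clinically relevant values become AEs (protocol 5.1) and all results are listed. True, but neither restores a superseded original to the DAIDS-graded incidence.

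**Vital signs left alone.** SAP 9.4 has similar last-repeat wording, and only the hypertension row of Appendix 3 asks for the lowest reading after repeats. This is fair as far as it goes. However, protocol 3.7.6.3 states no abnormality-driven repeat for vital signs, so the mechanism is less clear there.

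**Conclusion.** The point holds in conditional form and is minor. The stated rules permit replacement according to outcome. For QTcF, the by-visit change can be understated in an arm with a true rise: by 0 to 0.9 msec at 10 msec and 0 to about 1.5 msec (grid maximum 1.55) at 20 msec. With no true rise and a fixed threshold it is about 0, and it is negligible if repeats occur only near 500 msec. These sizes rest on assumed variability and thresholds. A trigger based on rise from baseline could take the figure to about 3 msec.

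The laboratory rule is the firmer part, because SAP 9.3 as worded can remove an abnormal original from a primary safety incidence. For ECG incidence the text needs clarifying more than correcting.

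It would be wrong to extend the point to the exposure-QT analysis, which uses Holter data (SAP 11), or to the QTcF > 500 msec withdrawal rule (protocol 3.8.3.2). Neither is affected.

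**What to change.** In SAP 9.6 and 9.3:
1. Use the original scheduled value in by-visit summaries unless it is technically invalid. For ECG this is the triplicate mean, Day -1 included.
2. Base the Appendix 4 ECG incidence and the DAIDS laboratory incidence on the worst post-baseline value among original, repeat and unscheduled results.
3. Footnote each incidence table with the number of subjects whose abnormality was confirmed on repeat.

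This costs a few sentences, with no new data and no protocol amendment. The drawback is that incidence will include some values that a repeat did not confirm, which the footnote makes visible.
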